**Table 8: DCC-2618 Dose Modifications for Dermatologic Toxicities (except Alopecia) and Arthralgia/Myalgia**

Toxicity Grade 	Dose Modification Guide
Grade 1	Institute support measures and continue DCC-2618 at the current dose
Grade 2	Institute support measures and continue DCC-2618 at the current dose If no improvement within 7 days, then interrupt DCC-2618 
 
• If the event returns to Grade 1 or baseline within 7 days, resume DCC-2618 at the same dose level
 
• If the event returns to Grade 1 or baseline after 7 days, resume DCC-2618 at a reduced dose level
 
 If this is a recurrence, after event returns to Grade 1 or baseline, resume DCC-2618 at a reduced dose level regardless of time to improvement If after a dose reduction the event is maintained at Grade 1 or baseline for at least 1 cycle (42 days) of dosing, consider re-escalating DCC-2618 by 1 dose level
Grade 3	Institute support measures Interrupt DCC-2618 for at least 7 days or until the event returns to Grade 1 or baseline (maximum 28 days) 
 
• Resume DCC-2618 at a reduced dose level
 
 If after a dose reduction the event is maintained at Grade 1 or baseline for at least 1 cycle (42 days) of dosing, consider re-escalating DCC-2618 by 1 dose level
Grade 4	Discontinue DCC-2618 unless the event is not considered life-threatening. Patients may continue DCC-2618 with non-life threatening events upon discussion with the Sponsor.
Grade: Any	Stevens-Johnson Syndrome / Hypersensitivity Reaction: If a patient experiences Stevens-Johnson syndrome (SJS)/hypersensitivity reaction while being treated with DCC-2618, DCC-2618 must be permanently discontinued. The patient should be immediately referred to a hospital for clinical evaluation and supportive care/management per institutional guidelines. Re-administration of DCC-2618 is not allowed due to the risk of recurrent SJS/hypersensitivity reaction. Caution for recurrence of SJS with other similar agents (TKIs for GIST) is advised.
 The severity of an AE that does not appear in the CTCAE v.5.0 scale must be assessed according to the criteria in Table 12 .	

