## **5.4. Study Drug Dose Interruption and Modification**

Sunitinib dose interruption and modification will follow guidelines as per the approved package insert or institutional guidelines. PK-guided sunitinib dosing is not allowed. Upon resumption following a dose interruption, the Investigator must continue with the patient's original visit schedule calculated from Cycle 1 Day 1 (i.e. cycle day count is continuous and does not pause with a dose interruption). Clinic visits and assessments should continue during dose interruptions as per [Table 1](#) (schedule of assessments). Dose interruptions of longer than 28 consecutive days will result in the patient being discontinued from the study. If the patient is on 4 weeks on, 2 weeks off cycle, the 28 days is inclusive of the 2 weeks off.

DCC-2618 may be interrupted or modified (i.e. dose reduction) at the discretion of the Investigator at any time due to AE, to accommodate palliative treatment, or for other reasons after consultation with the Sponsor. An interruption must be limited to no more than 28 consecutive days. Upon resumption following a dose interruption, the Investigator must continue with the patient's original visit schedule calculated from Cycle 1 Day 1 (i.e. cycle day count is continuous and does not pause with a dose interruption). Clinic visits and assessments should continue during dose interruptions as per [Table 1](#) (schedule of assessments). Dose interruptions of longer than 28 consecutive days will result in the patient being discontinued from the study.

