**Table 7: DCC-2618 Dose Modifications and Management of Hypertension**

Toxicity Grade	Management Guideline*
Grade 1 Prehypertension (systolic BP 120-139 mm Hg or diastolic BP 80-89 mm Hg)	Continue BP monitoring Continue DCC-2618 at the current dose level
Grade 2 Systolic BP 140-159 mm Hg or diastolic BP 90-99 mm Hg Or Symptomatic increase by > 20 mm Hg (diastolic) or to > 140/90 mm Hg if previously within normal limits	Treat BP to achieve diastolic BP $\leq$ 90 mmHg and or systolic BP $\leq$ 140 mmHg 
 
• If BP was previously within normal limits, start antihypertensive monotherapy
 
• If patient is already on antihypertensive medication, titrate dose up
 
 Continue the DCC-2618 at the current dose level Hold DCC-2618 if symptomatic increase by 20 mmHg (diastolic BP) until symptoms resolve and diastolic BP $\leq$ 90 mmHg On resuming DCC-2618, continue at the same dose level
Grade 3 Systolic BP <math>\geq</math> 160 mm Hg or diastolic BP <math>\geq</math> 100 mm Hg Or More than 1 drug or more intensive therapy than previously indicated	Treat to achieve diastolic BP $\leq$ 90 mmHg and or systolic BP $\leq$ 140 mmHg 
 
• Start antihypertensive medication and/or
 
• Increase current antihypertensive medication and/or
 
• Add an additional antihypertensive medication
 
 If symptomatic, hold DCC-2618 until diastolic BP $\leq$ 90 mmHg and/or systolic BP $\leq$ 140 mmHg, and symptoms resolve On resuming DCC-2618, continue at the same dose level If BP is not controlled with addition of a new or more intensive therapy, reduce DCC-2618 by 1 dose level If Grade 3 hypertension recurs despite DCC-2618 dose reduction and antihypertensive therapy, reduce the DCC-2618 by 1 additional dose level
Grade 4 Life-threatening consequences (e.g. malignant hypertension, transient or permanent neurologic deficit, hypertensive crisis)	Treat BP per institutional guidelines Permanently discontinue DCC-2618

BP=blood pressure

\*If BP remains controlled for at least 28 days, DCC-2618 dose re-escalation is permitted at the Investigator's discretion.

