**Table 9: DCC-2618 Dose Modifications for Isolated Bilirubin Increased**

Toxicity Grade	Management Guideline
Grade 2	Interrupt DCC-2618 until toxicity resolves to Grade 1 or baseline (maximum 28 days); resume DCC-2618 at 100 mg.
Grade 3 or 4	Interrupt DCC-2618 until toxicity resolves to Grade 1 or baseline (maximum 28 days); otherwise permanently discontinue DCC-2618.  If the event returns to Grade 1 or baseline, resume DCC-2618 at 100 mg.  If the reduced dose is tolerated without recurrence of the event for at least 28 days, consider re-escalating DCC-2618.  If Grade 3 or higher toxicity recurs, discontinue DCC-2618 permanently.

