**Table 10: DCC-2618 Dose Modifications for Treatment Related Adverse Events Not Mentioned Above**

Toxicity Grade	Management Guideline
Any Grade 3 or 4	Interrupt DCC-2618 dosing until event has resolved to Grade 1 or baseline Once the AE returns to Grade 1 or baseline, reduce DCC-2618 by 1 dose level If a patient tolerates the reduced dose without recurrence of the event for at least 28 days, consider re-escalating the dose of DCC-2618 to the prior dose level
Asymptomatic/Not clinically significant Grade 3 or 4 laboratory AEs (including CPK and lipase) that persist ≤10 days	Closely monitor for clinical symptoms and continue DCC-2618 at the current dose level. Repeat labs within 10 days.
Asymptomatic/Not clinically significant Grade 3 or 4 laboratory AEs (including CPK and lipase) that persist >10 days	Closely monitor for clinical symptoms; for Grade 4 events, interrupt DCC-2618 until the event returns to Grade 3 Asymptomatic Grade 3 or Grade 4 elevations of plasma enzyme: lipase or CPK do not require dose interruption Once the AE returns to Grade 3, resume DCC-2618 at the current dose level or consider reducing by 1 dose level per Investigator discretion after discussion with the Sponsor.
Clinically Significant Grade 3 or 4 laboratory AEs (including CPK and lipase)	Interrupt the DCC-2618. If the Investigator assesses that restarting DCC-2618 is in the patient's best interest, the Sponsor must be contacted for discussion and determination if restarting is allowed.

AE=adverse event; CPK=creatinine phosphokinase

 The rules for dose modifications for laboratory AEs will be based on local laboratory results.

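### Table 8, Grade 3 row: the word *or* literally allows a reduced-dose restart after 7 days with the skin or muscle/joint event still at Grade 3

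*Protocol*

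**What the plan says.** Protocol Section 5.4.2, Table 8, covers dermatologic toxicities (except alopecia), arthralgia and myalgia in the DCC-2618 arm. Its Grade 3 row asks for supportive measures and then says "Interrupt DCC-2618 for at least 7 days or until the event returns to Grade 1 or baseline (maximum 28 days". The bullet beneath tells the site to restart at a reduced dose and attaches no condition. The row closes with a re-escalation line that begins "If after a dose reduction the event is maintained at Grade 1 or baseline for at least 1 cycle (42 days) of dosing".

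Three general rules also apply:

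- Section 5.4 caps a hold: "Dose interruptions of longer than 28 consecutive days will result in the patient being discontinued from the study".
- Section 5.4.2 lets the investigator interrupt or reduce at any time for adverse events, and asks that reductions be discussed with the Sponsor beforehand where possible.
- The text under Table 5 requires discontinuation if the event behind a dose modification has not returned to Grade 1 or baseline within one 42-day cycle. There is an exception: if the investigator judges the event not clinically significant, a reduced-dose restart may be considered after consulting the Sponsor.

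**The concern.** The row appears to mean a minimum of 7 days off drug together with resolution, but it joins the two as alternatives. A site following it to the letter could restart on day 7 in a patient whose event is still at Grade 3. The same row would then require interruption again, so the instruction contradicts itself for that patient.

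At stake is a short, avoidable re-exposure of a patient with an unresolved severe toxicity, probably followed by a second hold. Different sites, all compliant, could also treat the same event differently. No efficacy analysis depends on this row.

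**Working it through.** The plan states no figure here to reproduce. The check is a reading of the restart conditions side by side, followed by a count of the patients who might be affected.

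**1. Restart condition once drug has been held**

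| Place | Condition for restart |
|---|---|
| Table 8, Grade 3 | 7 days elapsed, *or* Grade 1/baseline reached |
| Table 8, Grade 2, slow resolution | Grade 1/baseline: "If the event returns to Grade 1 or baseline after 7 days, resume DCC-2618 at a reduced dose level" |
| Table 8, Grade 2, resolution within 7 days, or recurrence | Grade 1/baseline |
| Table 9, bilirubin Grade 3 or 4 | Grade 1/baseline: "Interrupt DCC-2618 until toxicity resolves to Grade 1 or baseline (maximum 28 days); otherwise permanently discontinue DCC-2618" |
| Table 10, general Grade 3 or 4 | Grade 1/baseline: "Interrupt DCC-2618 dosing until event has resolved to Grade 1 or baseline" |
| Table 10, persistent asymptomatic Grade 4 laboratory events | A different criterion: "Once the AE returns to Grade 3, resume DCC-2618 at the current dose level", or consider one level lower |
| Table 7, Grade 3 hypertension | A different criterion: "If symptomatic, hold DCC-2618 until diastolic BP" and/or systolic pressure reaches target and symptoms resolve |

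The last two rows show that Grade 1 or baseline is not a universal restart rule. The closest comparison is the Grade 2 row, which covers the same toxicities. There, every restart after a hold waits for resolution.

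**2. Does another rule close the gap?**

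- The Section 5.4 cap acts only on holds longer than 28 days, so a day-7 restart never meets it.
- The 42-day rule under Table 5 acts after the restart and has its own exception.
- Sponsor discussion is requested where possible; it is not a bar.
- Table 10 is limited to events not covered by the earlier tables, so it cannot supply the missing condition for a Table 8 event.

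None of these forbids the restart.

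**3. How many patients reach the row?**

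The input is Protocol Table 3, which covers 114 GIST patients at 150 mg once daily. Five of its terms fall under Table 8:

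- Grade 3 events: hand-foot syndrome 1, rash 0, dry skin 0, myalgia 0, arthralgia 0. Total 1.
- Grade 4 events: 0.

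Rate: 1/114 = 0.88%, with exact (Clopper-Pearson) 95% limits of 0.02% and 4.79%.

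Applied to the 213 patients planned for DCC-2618:

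- Expected: 213 × 0.0088 = 1.9, about 2 patients.
- Lower limit: 213 × 0.0002 = about 0.05.
- Upper limit: 213 × 0.0479 = 10.2.

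This counts everyone expected to reach the Grade 3 row. The wording matters only for those still unresolved at day 7 whose investigator restarts anyway. The documents give no basis for estimating that subset, but it cannot be larger.

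**The case against.** The strongest reply is that Table 8 is a guide used alongside investigator judgement and does not insist on Grade 1 before dosing. Its Grade 2 row first continues full dose and holds only if there is no improvement within 7 days. Its Grade 4 row lets patients with events that are not life-threatening continue after discussion with the Sponsor. A patient whose Grade 3 event has fallen to Grade 2 by day 7 and who restarts at a reduced dose is therefore treated no more permissively than a patient with a new Grade 2 event on full dose. The exception under Table 5 also shows that the protocol accepts some reduced-dose treatment with an incompletely resolved event.

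Much of this stands. A reader might infer that Table 8 is simply looser at Grade 3 than at Grade 2. The documents do not support that: Grade 3 brings an immediate hold and a lower dose, and the contrast holds only for Grade 2 events already on hold. A reader might also infer that the sponsor meant to allow re-dosing of unresolved Grade 3 events. The 28-day maximum and the re-escalation line, which presupposes an event at Grade 1 or baseline, point the other way, although neither settles it.

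The literal permission to restart before day 7 after early resolution is not a safety problem either, since the Grade 2 row allows the same.

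What the reply does not answer is the patient still at Grade 3 on day 7. For that patient the row permits a restart and requires a hold at once.

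**Conclusion.** The concern holds as a minor safety-wording error. The Grade 3 row literally permits a reduced-dose restart after 7 days with the event still at Grade 3, and no other provision prevents it.

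At most about 2 of 213 patients (range about 0 to 10) are expected to reach the row, and fewer would be restarted unresolved. It would be a mistake to read the figure of 2 as the number re-dosed with an active Grade 3 event. It assumes that the Phase 1 rate at 150 mg carries over, and it rests on a single event. Table 3 omits terms below 10% incidence, so the true rate could be somewhat higher.

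The harm is limited by the reduced dose, by the renewed hold that the row itself requires, and later by the 42-day rule. Efficacy, alpha and power are unaffected.

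**What to change.** Change the conjunction and make the restart follow from it, for example: *Hold DCC-2618 for a minimum of 7 days and until Grade 1 or baseline is reached (maximum 28 days); then restart at a reduced dose level.*

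Add no new discontinuation clause. Events unresolved at day 28 should stay under Section 5.4 and the text under Table 5, including the Sponsor-consultation exception for events judged not clinically significant. A clause forcing discontinuation at day 28 would override that exception for this row.

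The change is one line in a clarification or the next amendment, with no added procedures or visits. It does have a price for patients. A few will be held longer, including any whose event resolves before day 7. Occasionally a patient whose event improves slowly, who could now restart before day 28, will instead reach the existing limit and be discontinued.

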**Table 9: DCC-2618 Dose Modifications for Isolated Bilirubin Increased**

Toxicity Grade	Management Guideline
Grade 2	Interrupt DCC-2618 until toxicity resolves to Grade 1 or baseline (maximum 28 days); resume DCC-2618 at 100 mg.
Grade 3 or 4	Interrupt DCC-2618 until toxicity resolves to Grade 1 or baseline (maximum 28 days); otherwise permanently discontinue DCC-2618.  If the event returns to Grade 1 or baseline, resume DCC-2618 at 100 mg.  If the reduced dose is tolerated without recurrence of the event for at least 28 days, consider re-escalating DCC-2618.  If Grade 3 or higher toxicity recurs, discontinue DCC-2618 permanently.

**Table 10: DCC-2618 Dose Modifications for Treatment Related Adverse Events Not Mentioned Above**

Toxicity Grade	Management Guideline
Any Grade 3 or 4	Interrupt DCC-2618 dosing until event has resolved to Grade 1 or baseline Once the AE returns to Grade 1 or baseline, reduce DCC-2618 by 1 dose level If a patient tolerates the reduced dose without recurrence of the event for at least 28 days, consider re-escalating the dose of DCC-2618 to the prior dose level
Asymptomatic/Not clinically significant Grade 3 or 4 laboratory AEs (including CPK and lipase) that persist ≤10 days	Closely monitor for clinical symptoms and continue DCC-2618 at the current dose level. Repeat labs within 10 days.
Asymptomatic/Not clinically significant Grade 3 or 4 laboratory AEs (including CPK and lipase) that persist >10 days	Closely monitor for clinical symptoms; for Grade 4 events, interrupt DCC-2618 until the event returns to Grade 3 Asymptomatic Grade 3 or Grade 4 elevations of plasma enzyme: lipase or CPK do not require dose interruption Once the AE returns to Grade 3, resume DCC-2618 at the current dose level or consider reducing by 1 dose level per Investigator discretion after discussion with the Sponsor.
Clinically Significant Grade 3 or 4 laboratory AEs (including CPK and lipase)	Interrupt the DCC-2618. If the Investigator assesses that restarting DCC-2618 is in the patient's best interest, the Sponsor must be contacted for discussion and determination if restarting is allowed.

AE=adverse event; CPK=creatinine phosphokinase

 The rules for dose modifications for laboratory AEs will be based on local laboratory results.

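### Table 9's bilirubin hold covers only undefined 'isolated' increases, so a rise with raised ALT/AST depends on reading and discretion; its fixed 100 mg restart can double a 50 mg dose

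*Protocol*

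**What the plan says.** Protocol Sections 5.4 and 5.4.2 let the Investigator interrupt or reduce DCC-2618 at any time because of an adverse event. Section 5.4.2 presents Tables 6 to 10 as guidelines. Under Section 5.4, more than 28 consecutive days off drug ends participation.

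Table 9 is headed "DCC-2618 Dose Modifications for Isolated Bilirubin Increased". Its Grade 2 row reads "Interrupt DCC-2618 until toxicity resolves to Grade 1 or baseline (maximum 28 days); resume DCC-2618 at 100 mg". Its Grade 3-4 row also interrupts for at most 28 days, discontinues if there is no recovery, and restarts at 100 mg. Neither the protocol nor the SAP defines 'isolated'.

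Table 10 is headed "DCC-2618 Dose Modifications for Treatment Related Adverse Events Not Mentioned Above". It has four rows, all limited to Grade 3 or 4:

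- Any event: "Interrupt DCC-2618 dosing until event has resolved to Grade 1 or baseline", then reduce by one level.
- Asymptomatic or not clinically significant laboratory event, up to 10 days: "Closely monitor for clinical symptoms and continue DCC-2618 at the current dose level. Repeat labs within 10 days".
- The same, beyond 10 days: "for Grade 4 events, interrupt DCC-2618 until the event returns to Grade 3", then "resume DCC-2618 at the current dose level or consider reducing by 1 dose level per Investigator discretion after discussion with the Sponsor". No hold is stated for Grade 3.
- Clinically significant laboratory event: interrupt, with the Sponsor deciding whether a restart is allowed.

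The two middle rows cover asymptomatic or not "clinically significant Grade 3 or 4 laboratory AEs (including CPK and lipase"; the two enzymes are included, but the rows are not limited to them. The one explicit statement that no interruption is needed names lipase and CPK, and the rationale in Section 1.3.2.1 concerns lipase. No dose-modification table names ALT or AST.

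**The concern.** Clinically, bilirubin raised together with transaminases would be expected to call for at least as much caution as bilirubin raised alone. That is general judgement, which the documents do not state. On one natural reading the tables do the reverse: raised ALT/AST takes a Grade 2 patient out of the table with a written hold and into one with no row for Grade 2.

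The question will arise from entry in some patients. Inclusion criterion 9 admits AST/ALT up to 3 x ULN, or 5 x ULN with hepatic metastases. In such a patient it is unclear whether a later bilirubin rise is 'isolated', and two of the roughly 125 centers could treat identical values differently.

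At stake are patient safety and consistent dosing in the DCC-2618 arm. Nothing here bears on the validity of the PFS, ORR or OS analyses.

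**Working it through.** The plan gives no figure to reproduce. The check takes a treatment-related bilirubin rise and asks which row applies.

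**Step 1: match cases to rows.**

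| Case | Table 9 | Table 10 |
|---|---|---|
| Grade 2 bilirubin alone | Hold, restart at 100 mg | Not needed |
| Grade 2 bilirubin, ALT/AST raised but below Grade 3 | Hold if 'isolated' tolerates raised ALT/AST; otherwise nothing | 0 of 4 rows |
| Grade 2 bilirubin, ALT/AST at Grade 3-4 | Same question | ALT/AST qualifies in its own right |
| Grade 3-4 combined, judged asymptomatic or not clinically significant, up to 10 days | Same question | General row interrupts; laboratory row continues |
| The same, beyond 10 days | Same question | General row holds to Grade 1 or baseline; laboratory row holds Grade 4 only, to Grade 3 |
| Grade 3-4 combined, clinically significant | Same question | Interrupt; Sponsor decides on restart |

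Table 10 does not say which row prevails where two apply.

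**Step 2: how far Section 7.7.1 narrows the Grade 3-4 overlap.** One criterion is enough for clinical significance. Needing further diagnostic testing is one; withholding drug is another. A repeat test alone does not qualify. A Grade 3-4 combined rise that prompts work-up beyond a repeat is therefore clinically significant and interrupted. Sections 7.7.1 and 7.11 also favour recording a diagnosis over separate laboratory findings, and a Grade 3-4 liver diagnosis meets the general row. What remains is a Grade 3-4 combined rise recorded as a laboratory event and judged to need nothing beyond a repeat. One ambiguity stays: if the slash in the middle rows' scope means 'or', an asymptomatic result that is clinically significant also fits them.

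**Step 3: restart dose.** Table 5 gives 150, 100 and 50 mg. Against Table 9's fixed 100 mg:

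- onset at 150 mg: 100/150 = 0.67, a reduction;
- onset at 100 mg: 100/100 = 1, no change;
- onset at 50 mg: 100/50 = 2, a doubling.

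**Step 4: next scheduled chemistry if no row prompts a repeat.** Table 1 schedules chemistry on Days 1, 15 and 29 of Cycle 1, Days 1 and 29 of Cycle 2, and Day 1 only from Cycle 3. With 42-day cycles the nominal gaps are 14 days in Cycle 1, 28 then 14 in Cycle 2, and 42 from Cycle 3. These are the planned minimum; Section 6.6 allows unscheduled tests at any time.

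**Step 5: ceiling on frequency.** Protocol Table 3 lists events in at least 10% of 114 GIST patients at 150 mg. No bilirubin, ALT or AST term appears. Since 12/114 = 10.5% would be listed and 11/114 = 9.6% would not, each such term occurred in at most 11 patients. Assuming bilirubin rises were coded to one term and the rate carries over, 213 x 11/114 = 20.6. Combined rises are a subset, so the range is 0 to about 21 at any grade, and lower at Grade 2 or above.

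**The case against.** The strongest reply is that the Investigator can already act. Sections 5.4 and 5.4.2 allow a hold at any grade, unscheduled tests are permitted, and Section 6.11.7 and the Table 10 footnote base dose decisions on local results, so the scheduled visits do not limit when a site can respond. This stands. A reader might infer that patients with a combined rise are unprotected or must stay on drug; the documents do not support that. The gap is in written guidance. Yet the same discretion existed for isolated bilirubin, and the sponsor still wrote a rule.

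Second, a site could apply Table 9 as the only bilirubin table, and then there is no Grade 2 gap. This also stands, so the gap is conditional. On that reading, though, 'isolated' does no work and the heading should say so.

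Third, the Grade 3-4 overlap is small because of Section 7.7.1. Largely accepted. One could add that specific rows prevail over general ones, as Section 1.3.2.1 shows for asymptomatic lipase. For liver tests that produces the permissive outcome, with no rationale offered.

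Fourth, the text under Table 5 permits a return from 50 to 100 mg after recovery. It addresses the event that led to the reductions, and its stated aim is the dose at which the event occurred. For bilirubin arising on 50 mg, that is 50 mg.

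Finally, no combined case is shown and the lower bound is zero. That limits the weight of the point but does not answer it.

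**Conclusion.** The point holds in a limited form, and the wording is worth correcting.

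- **Grade 2:** if 'isolated' excludes raised ALT/AST, a combined rise with neither value at Grade 3 has no row and rests on discretion. A reader might call this gap unconditional; it is not, because an undefined word decides it.
- **Grade 3-4:** two rows conflict for a combined rise judged asymptomatic or not clinically significant. It would be too strong to say the plan continues drug through Grade 3-4 combined rises in general, since most that prompt any work-up are interrupted.
- **Restart dose:** read literally, Table 9 doubles the dose of a patient on 50 mg at onset. This does not depend on the meaning of 'isolated' in combined cases.

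Frequency is unknown. About 21 of 213 is a ceiling resting on the two assumptions in the working; it is not an estimate of affected patients.

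**What to change.** Make three edits in the next amendment.

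1. **Table 10.** State that the two asymptomatic/not clinically significant laboratory rows do not apply to bilirubin raised together with ALT/AST.
2. **Table 9 restart.** Replace the fixed dose with 100 mg, or the dose at onset if that was lower.
3. **Table 9 scope.** Define 'isolated' as bilirubin increased without ALT/AST above a named limit. The criterion 9 limits (3 x ULN, or 5 x ULN with hepatic metastases) are one candidate, taken relative to baseline if raised at entry; the sponsor's safety physicians should settle the value. For Grade 2 or higher bilirubin with ALT/AST above that limit, apply at least the Table 9 hold: interrupt until Grade 1 or baseline, at most 28 days, otherwise discontinue. Require Sponsor determination before restart after Grade 3-4, and write it into this rule, because Table 10 covers only events not already named. Every bilirubin increase that calls for action then falls under one rule or the other.

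No scheduled tests are added: bilirubin, ALT and AST are already in the Table 11 panel. Section 11.2 requires ethics and regulatory approval, across about 125 centers, which is why the edits should travel with an amendment made for other reasons.

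The clinical cost is a few more dose holds. If resumption must be at a reduced dose, patients already on 50 mg would have no lower level and would be discontinued under Section 5.4.2. For Grade 2 events this can be avoided by allowing resumption at 50 mg after discussion with the Sponsor.
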